## 10.9.6. Safety Figures

Safety:	Safety: Tables					
No.	p. Population IDSL / Example Shell Title Programming Notes Programming Notes Programming Notes					
ECG						
2.1.	Safety	EG9	Mean (95% CI) Change from Baseline in QTcF Interval by Timepoint and Treatment		SAC	

## 10.9.7. Pharmacokinetic Tables

Pharm	Pharmacokinetic: Tables						
No.	Population	IDSL / Example Shell	Title	Programming Notes	Deliverable [Priority]		
PK Concentration Data							
3.1.	PK Concentration	PKCT1	Summary of Tenofovir Alafenamide (TAF) Plasma Pharmacokinetic Concentration-Time Data (units) by Treatment		SAC		
3.2.	PK Concentration	PKCT1	Summary of Tenofovir (TFV) Plasma Pharmacokinetic Concentration-Time Data (units) by Treatment		SAC		
3.3.	PK Concentration	PKCT1	Summary of Emtricitabine (FTC) Plasma Pharmacokinetic Concentration-Time Data (units) by Treatment		SAC		
3.4.	PK Concentration	PKCT1	Summary of GSK3640254 Plasma Pharmacokinetic Concentration-Time Data (units) by Treatment		SAC		
3.5.	PK Concentration	PKCT1	Summary of Predose (trough) Tenofovir Alafenamide (TAF) Plasma Concentration Data (units) by Treatment		SAC		
3.6.	PK Concentration	PKCT1	Summary of Predose (trough) Tenofovir (TFV) Plasma Concentration Data (units) by Treatment		SAC		
3.7.	PK Concentration	PKCT1	Summary of Predose (trough) Emtricitabine (FTC) Plasma Concentration Data (units) by Treatment		SAC		
3.8.	PK Concentration	PKCT1	Summary of Predose (trough) GSK3640254 Plasma Concentration Data (units) by Treatment		SAC		
PK Dei	rived Parameters	3					
3.9.	PK Parameter	PKPT4	Summary Statistics of Derived Tenofovir Alafenamide (TAF) Plasma Pharmacokinetic Parameters (Non-Transformed) Based on Actual Time by Treatment	Parameters with units	SAC		
3.10.	PK Parameter	PKPT4	Summary Statistics of Derived Tenofovir Alafenamide (TAF) Plasma Pharmacokinetic Parameters (Ln-Transformed) Based on Actual Time by Treatment	Parameters with units	SAC		

Pharma	acokinetic: Tabl	es			
No.	Population	IDSL / Example Shell	Title	Programming Notes	Deliverable [Priority]
3.11.	PK Parameter	PKPT4	Summary Statistics of Derived Tenofovir (TFV) Plasma Pharmacokinetic Parameters (Non-Transformed) Based on Actual Time by Treatment	Parameters with units	SAC
3.12.	PK Parameter	PKPT4	Summary Statistics of Derived Tenofovir (TFV) Plasma Pharmacokinetic Parameters (Ln-Transformed) Based on Actual Time by Treatment	Parameters with units	SAC
3.13.	PK Parameter	PKPT4	Summary Statistics of Derived Emtricitabine (FTC) Plasma Pharmacokinetic Parameters (Non-Transformed) Based on Actual Time by Treatment	Parameters with units	SAC
3.14.	PK Parameter	PKPT4	Summary Statistics of Derived Emtricitabine (FTC) Plasma Pharmacokinetic Parameters (Ln-Transformed) Based on Actual Time by Treatment	Parameters with units	SAC
3.15.	PK Parameter	PKPT4	Summary Statistics of Derived GSK3640254 Plasma Pharmacokinetic Parameters (Non-Transformed) Based on Actual Time by Treatment	Parameters with units	SAC
3.16.	PK Parameter	PKPT4	Summary Statistics of Derived GSK3640254 Plasma Pharmacokinetic Parameters (Ln-Transformed) Based on Actual Time by Treatment	Parameters with units	SAC
PK Ana	lysis Tables				
3.17.	PK Parameter	PKPT3	Statistical Analysis of Tenofovir Alafenamide (TAF) Plasma Pharmacokinetic Parameters: Analysis of Variance (ANOVA)	AUC(0-τ), Cτ, and Cmax	SAC
3.18.	PK Parameter	PKPT3	Statistical Analysis of Tenofovir (TFV) Plasma Pharmacokinetic Parameters: Analysis of Variance (ANOVA)	AUC(0-τ), Cτ, and Cmax	SAC
3.19.	PK Parameter	PKPT3	Statistical Analysis of Emtricitabine (FTC) Plasma Pharmacokinetic Parameters: Analysis of Variance (ANOVA)	AUC(0-τ), Cτ, and Cmax	SAC

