# 2.2.4. Tenofovir Alafenamide/Emtricitabine

Descovy (tenofovir alafenamide/emtricitabine) was first approved in the United States (US) in 2015 [DESCOVY US Prescribing Information, 2017]. Tenofovir

alafenamide/emtricitabine are both HIV nucleoside analog reverse transcriptase inhibitors. Tenofovir alafenamide and emtricitabine are rapidly and extensively absorbed following oral administration with peak plasma concentrations occurring at 1 to 3 hours after dose.

Tenofovir alafenamide has a 0.51-hour median plasma half-life with a mean plasma Cmax and AUC from time 0 to the end of the dosing interval at steady state (AUC[0- $\tau$ ]) of 0.16 µg/mL and 0.21 µg*h/mL, respectively, after repeat dosing under fed conditions. The pharmacologically active metabolite of the TAF prodrug is tenofovir (TFV), which has a mean plasma Cmax and AUC(0- $\tau$ ) of 0.02 µg/mL and 0.29 µg*h/mL, respectively, after repeat dosing under fed conditions. Emtricitabine has a 10-hour median plasma half-life with a mean plasma Cmax and AUC(0- $\tau$ ) of 2.1 µg/mL and 11.7 µg*h/mL, respectively, after repeat dosing under fed conditions. Both FTC and TFV are subsequently phosphorylated intracellularly, resulting in very long (approximately 2 to 6 days) intracellular half-lives. In addition, TAF/FTC lacks many of the associated drug interactions, specifically with oral contraceptives, statins, antidepressants, anxiolytics, anticoagulants, and other medications commonly taken by HIV-positive patients. For more details, please reference the current Descovy label [DESCOVY US Prescribing Information, 2017].

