# 3. OBJECTIVES AND ENDPOINTS

Objective	Endpoint

 
Primary
 
To assess the effect of GSK3640254 on the PK of TAF, FTC, and the active metabolite of TAF prodrug, TFV under fed conditions in healthy participants
 
	
 
AUC(0-τ) and Cmax for TAF
 
AUC(0-τ), Cmax, and Cτ for FTC and TFV
 

 
Secondary
 
To assess the safety and tolerability of
 
	
 
Safety and tolerability parameters for
 

TAF/FTC administered alone and when coadministered with GSK3640254 in healthy participants	AEs/SAEs, observed and change from baseline clinical laboratory assessments, ECGs, and vital sign measurements
• To characterize the steady-state PK of GSK3640254 in the presence of TAF/FTC in healthy participants	
 
AUC(0-τ), Cmax, Cτ, and Tmax for GSK3640254
 

• To characterize the steady-state PK of TAF, FTC, and TFV alone and in combination with GSK3640254 in healthy participants	
 
Tmax for TAF, FTC, and TFV
 

AE = adverse event; AUC  $(0-\tau)$  = area under the plasma concentration-time curve from time 0 to the end of the dosing interval at steady state; Cmax = maximum observed concentration; C $\tau$  = Plasma concentration at the end of the dosing interval; ECG = electrocardiogram; FTC = emtricitabine; PK = pharmacokinetics; SAE = serious adverse event; TAF = tenofovir alafenamide; TFV = tenofovir; Tmax = time of maximum observed concentration.

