# 4.3. Justification for Dose

The doses of 200 mg GSK3640254 and 25/200 mg TAF/FTC were selected for this study. The maximum projected clinical dose of GSK3640254 is 200 mg QD. The apparent terminal phase half-life (t1/2) of GSK3640254 was approximately 22 hours in the MAD portion of Study 207187 at the 200-mg dose, and predicted time to steady state is approximately 5 days. Tenofovir alafenamide/emtricitabine 25/200 mg QD was selected for this study because it is the currently recommended dose for HIV-infected patients. The t1/2 of TAF is approximately 0.5 hours and the t1/2 of FTC is approximately 10 hours.

Dosing of GSK3640254 QD from Period 2, Days 1 to 7 should be sufficient to bring plasma concentrations to steady state. There is no subsequent need for a washout of

GSK3640254 since the primary remaining evaluation is for coadministered TAF/FTC and GSK3640254 at steady state.

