### 7.2.4. Statistical Analyses / Methods

Details of the planned displays are provided in Appendix 9: List of Data Displays and will be based on GSK Data Standards and statistical principles.

Unless otherwise specified, endpoints/variables defined in Section 7.2.1 will be summarized using descriptive statistics, graphically presented (where appropriate) and listed.

Secondary plasma PK parameters (Tmax) will be estimated for TAF, FTC, and TFV (Periods 1 and 2) and secondary plasma PK parameters AUC(0- $\tau$ ), C $\tau$ , Cmax, and Tmax will be estimated for GSK3640254 (Period 2). Summary statistics (arithmetic mean, geometric mean, median, standard deviation, minimum, maximum, and coefficient of variation) for plasma GSK3640254 and TAF, FTC, and TFV PK parameter values will be summarized by treatment.

Predose (trough) PK plasma concentrations (TAF, FTC, and TFV: Days 2 through 14 [Period 1] and Days 1 through 7 [Period 2]; GSK3640254: Days 2 through 7 [Period 2]) will be summarized using the PK Concentration Population, and used to assess achievement of steady state.

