## 10.3.3. Reporting Standards for Pharmacokinetics

Pharmacokinetic Con	centration Data
Descriptive Summary Statistics, Graphical Displays and Listings	Refer to IDSL PK Display Standards. Refer to IDSL Statistical Principle 6.06.1. For continuous data:  NQs at the beginning of a participant profile (i.e. before the first incidence of a measurable concentration) are deemed to be zero as it is assumed that in this circumstance no drug is yet measurable in the blood. For NQs at the end of the participant profile (i.e. after the last incidence of a measurable concentration); for individual plots and pharmacokinetic analyses these are dropped (set to missing) as they do not provide any useful information (and can erroneously indicate that absolutely no drug is present) for summary statistics, these are set to 0 (to avoid skewing of the summary statistics) Individual NQs which fall between two measurable concentrations are set to missing (individual values of this nature are assumed to be an anomaly) If two or more NQ values occur in succession between measurable concentrations, the profile will be deemed to have terminated at the last measurable concentration prior to these NQs. For the purpose of individual participant plots, these NQs will be set to 0, and the subsequent measurable concentrations will be retained. For the derivation of pharmacokinetic parameters, these NQs and any subsequent measurable concentrations will be omitted (set to missing).  Note: Concentration values will be imputed as per GUI_51487 for descriptive summary statistics/analysis and summarized graphical displays only.
Pharmacokinetic Para	
Descriptive Summary Statistics, Graphical Displays and Listings	N, n, geometric mean, 95% CI of geometric mean, SD of logged data and between subject geometric coefficient of variation (CVb (%)) will be reported. $ \text{CV}_b\left(\%\right) = \sqrt{\left(\text{exp}(\text{SD}^2) - 1\right) * 100} $ (SD = SD of Ln-Transformed data)
Parameters Not Being Ln- Transformed	Tmax, λz, λz lower, λz upper, and λz no. of points.

Parameters Not Being Summarized	λz, λz lower, λz upper, and λz no. of points.
Listings	Include the first point, last point and number of points used in the determination of λz and Rsq_adjusted for listings.

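### Does listing Cτ for TAF in SAP Table 3.17, and using TAF troughs to judge steady state, put any result of the study at risk?

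*SAP*

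**What the plan says.** Protocol section 3 gives the primary endpoints for TAF as "AUC(0-τ) and Cmax for TAF" and reserves Cτ for FTC and TFV. Protocol 9.4.1, SAP 2.2 and SAP 7.1.4 make the same split.

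In SAP 10.9.7, Table 3.17 is titled "Statistical Analysis of Tenofovir Alafenamide (TAF) Plasma Pharmacokinetic Parameters: Analysis of Variance (ANOVA"), and its programming note reads "AUC(0-τ), Cτ, and Cmax". Tables 3.18 (TFV) and 3.19 (FTC) carry the identical note. The model text in SAP 2.4 and 7.1.4.1 refers to the logarithms of all three parameters and names TAF, FTC and TFV in the period comparison, without excepting TAF Cτ. SAP 2.1 reports no changes from the protocol's analysis.

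On troughs, SAP 7.2.4 says that pre-dose concentrations, TAF included, "will be summarized using the PK Concentration Population, and used to assess achievement of steady state". Protocol 9.4.1 contains the same plan.

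On the drug itself, Protocol 2.2.4 states: "Tenofovir alafenamide has a 0.51-hour median plasma half-life". Protocol 4.3 agrees: "The t1/2 of TAF is approximately 0.5 hours and the t1/2 of FTC is approximately 10 hours".

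**The concern.** A programmer working from the display list would fit a Period 2 versus Period 1 model to the logarithm of TAF Cτ. The protocol does not ask for that ratio, and the drug's half-life leaves nothing to measure at 24 h. The primary table would then hold either an empty row or, worse, a ratio built from the few values that appeared through carry-over, a mislabelled tube or a dosing error. SAP 10.3.3 adds to the worry. For non-quantifiable values at the end of a profile it says "for summary statistics, these are set to 0 (to avoid skewing of the summary statistics"), and the logarithm of zero does not exist.

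The troughs raise a related point. If every pre-dose TAF value is below the assay limit, Table 3.5 and Figure 3.17 say nothing about steady state, yet a row of constant zeros could be read as a check that was passed. At stake would be the content of a primary-analysis table and the evidence that the two profiles were taken at steady state.

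**Working it through.** **Inputs.** From Protocol 2.2.4: TAF half-life 0.51 h, mean Cmax 0.16 µg/mL (160 ng/mL), peak at 1 to 3 h; FTC half-life 10 h, Cmax 2.1 µg/mL; TFV Cmax 0.02 µg/mL, AUC(0-τ) 0.29 µg·h/mL. From Protocol 4.3: TAF half-life about 0.5 h. From the Schedule of Activities: the last serial samples are at 8, 12 and 24 h. No lower limit of quantification (LLOQ) is given for TAF; 0.001 to 5 ng/mL is assumed.

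**The plan's own precision figure (Protocol 9.2.1).** Half-width = t(0.95, 11) × √ln(1 + 0.20²) × √(2/12) = 1.796 × 0.198 × 0.408 = 0.145, giving 0.865 to 1.156 at a ratio of 1.0. This matches the protocol. It was derived for AUC(0-τ) and Cmax, so a Cτ row does not enter it.

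**TAF at 24 h.** With mono-exponential decline from the peak, C24 = 160 × 2^−((24 − Tmax)/t½).

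| t½ (h) | Tmax (h) | Half-lives after peak | C24 (ng/mL) |
|---|---|---|---|
| 0.50 | 1 | 46.0 | 2.3e-12 |
| 0.50 | 3 | 42.0 | 3.6e-11 |
| 0.51 | 1 | 45.1 | 4.2e-12 |
| 0.51 | 3 | 41.2 | 6.4e-11 |

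For C24 to reach an LLOQ of 1, 0.1, 0.01 or 0.001 ng/mL, the half-life would have to lengthen 5.6 to 6.2, 3.9 to 4.2, 2.9 to 3.2 or 2.4 to 2.6 fold. Even if GSK3640254 did this in Period 2, Period 1 is TAF/FTC alone and the denominator would still be missing.

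**What the SAP does with such values.** SAP 10.3.3 treats two uses separately. In summary statistics of concentrations, end-of-profile non-quantifiable values become 0. In pharmacokinetic analyses they are dropped. A TAF Cτ would therefore be missing, and ln(0) never reaches the model.

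**Could a stray 24 h value get through?** SAP 10.3.3 also ends a profile when two or more non-quantifiable values in a row lie between measurable ones, and omits later values from parameter derivation. Predicted TAF values are:

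- 8 h: 160 × 2^−(5/0.51) ≈ 0.18 ng/mL (peak at 3 h) or 160 × 2^−(7/0.51) ≈ 0.012 ng/mL (peak at 1 h).
- 12 h: 160 × 2^−(9/0.51) ≈ 0.0008 ng/mL or 160 × 2^−(11/0.51) ≈ 0.00005 ng/mL.

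For any LLOQ above about 0.18 ng/mL, both 8 h and 12 h are non-quantifiable and a stray 24 h value is discarded. With a more sensitive assay and a late peak, 8 h may be measurable. Only the 12 h value is then missing, and a stray value could survive. SAP 7.1.4.1 still runs the models only if profiles are well defined and data are sufficient, and a ratio needs values in both periods.

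**Troughs.** There are 13 (Period 1, Days 2 to 14) + 7 (Period 2, Days 1 to 7) = 20 pre-dose samples per participant. TAF accumulation is 1/(1 − 2^−(24/0.51)) = 1.000, so steady state holds from the first dose and troughs cannot add to that. For FTC, accumulation is 1/(1 − 2^−2.4) = 1.23 and C24 is 2.1 × 2^−2.3 = 0.43 to 2.1 × 2^−2.1 = 0.49 µg/mL. For TFV, the average concentration is 0.29/24 = 0.012 µg/mL, about 60% of its Cmax, so the profile is flat and its trough is informative.

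**Count of ratios.** Protocol: TAF 2 + FTC 3 + TFV 3 = 8. Display list as written: 9. Nothing is formally tested (Protocol 9.1), so the ninth has no multiplicity cost.

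**The case for a change.** The strongest case for a correction is traceability. A primary-analysis table lists a parameter that the protocol does not assign to that analyte, while SAP 2.1 reports no changes. The repair is a few words and needs no new samples. With a very sensitive assay and a late peak, the successive-value rule does not close every route for an anomalous Cτ. The trough plan for TAF is uninformative by the protocol's own half-life, and Figure 3.17 asks for a semi-logarithmic plot that cannot show zeros.

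The inconsistency stands, and so does the pharmacology. Three limits reduce its weight.

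- The SAP body text is right, and the note is identical to those for TFV and FTC, so it looks like a copy. An analyst has SAP 7.1.4 to settle it.
- The protocol leaves TAF Cτ out of its lists but does not forbid it, and the SAP allows additional parameters.
- The trough plan is the protocol's own, so a SAP-only edit would create a departure where none exists.

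The worry that zeros could pass for a check also has little force. A reader who took them as showing steady state for TAF would reach a correct conclusion. The steady state that matters in Period 2, that of GSK3640254, is judged from its own troughs in Table 3.8.

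**Conclusion.** The Table 3.17 note is a clerical slip, and the TAF trough summaries are uninformative but harmless. Followed exactly as written, the plan gives an empty or non-estimable TAF Cτ row, a table of zeros for TAF troughs, and a semi-log panel with nothing to draw. The eight protocol ratios, their 90% intervals and the half-width of 0.145 are unaffected. Steady state for FTC, TFV and GSK3640254 is still assessed from their own troughs. Deleting a word from the note would be tidier but would improve no estimate or conclusion, so no change is called for.

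This rests on mono-exponential decline at the stated half-life and on an assumed LLOQ between 0.001 and 5 ng/mL. The margin is wide: even at the lowest assumed limit, the half-life would have to be at least 2.4 times the stated value before a 24 h TAF concentration could be measured.

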## 10.9.8. Pharmacokinetic Figures

Pharm	acokinetic: Figu	res			
No.	Population	IDSL / Example Shell	Title	Programming Notes	Deliverable [Priority]
Individ	ual Concentration	on Plots			•
3.1.	PK Concentration	PKCF1P	Individual Tenofovir Alafenamide (TAF) Plasma Concentration- Time Plots by Participant (Linear and Semi-Logarithmic)	Paginate by Participant Dashed line represents the LLQ Periods Overlaid	SAC
3.2.	PK Concentration	PKCF1P	Individual Tenofovir (TFV) Plasma Concentration-Time Plots by Participant (Linear and Semi-Logarithmic)	Paginate by Participant Dashed line represents the LLQ Periods Overlaid	SAC
3.3.	PK Parameter	PKCF2	Individual Emtricitabine (FTC) Plasma Concentration-Time Plots by Participant (Linear and Semi-Logarithmic)	Periods Overlaid	SAC
3.4.	PK Concentration	PKCF2	Individual GSK3640254 Plasma Concentration-Time Plots by Participant (Linear and Semi-Logarithmic)	Periods Overlaid	SAC
3.5.	PK Parameter	PKCF2	Individual Tenofovir Alafenamide (TAF) Plasma Concentration- Time Plots by Treatment (Linear and Semi-Logarithmic)	Periods Overlaid	SAC
3.6.	PK Parameter	PKCF2	Individual Tenofovir (TFV) Plasma Concentration-Time Plots by Treatment (Linear and Semi-Logarithmic)	Periods Overlaid	SAC
3.7.	PK Concentration	PKCF2	Individual Emtricitabine (FTC) Plasma Concentration-Time Plots by Participant (Linear and Semi-Logarithmic)	Periods Overlaid	SAC
3.8.	PK Concentration	PKCF1P	Individual GSK3640254 Plasma Concentration-Time Plots by Treatment (Linear and Semi-Logarithmic)	Periods Overlaid	SAC
Mean /	Median Concen	tration Plots			
3.9.	PK Concentration	PKCF1P	Mean (± Standard Deviation) Tenofovir Alafenamide (TAF) Plasma Concentration-Time Plots by Treatment (Linear and Semi-Logarithmic)	Periods Overlaid	SAC

Pharma	Pharmacokinetic: Figures						
No.	Population	IDSL / Example Shell	Title	Programming Notes	Deliverable [Priority]		
3.10.	PK Concentration	PKCF1P	Mean (± Standard Deviation) Tenofovir (TFV) Plasma Concentration-Time Plots by Treatment (Linear and Semi- Logarithmic)	Periods Overlaid	SAC		
3.11.	PK Concentration	PKCF1P	Mean (± Standard Deviation) Emtricitabine (FTC) Plasma Concentration-Time Plots by Treatment (Linear and Semi-Logarithmic)	Periods Overlaid	SAC		
3.12.	PK Concentration	PKCF2	Mean (± Standard Deviation) GSK3640254 Plasma Concentration-Time Plots by Treatment (Linear and Semi- Logarithmic)	Periods Overlaid	SAC		
3.13.	PK Concentration	PKCF3	Median (Range) Tenofovir Alafenamide (TAF) Plasma Concentration-Time Plots by Treatment (Linear and Semi- Logarithmic)	Periods Overlaid	SAC		
3.14.	PK Concentration	PKCF3	Median (Range) Tenofovir (TFV) Plasma Concentration-Time Plots by Treatment (Linear and Semi-Logarithmic)	Periods Overlaid	SAC		
3.15.	PK Concentration	PKCF3	Median (Range) Emtricitabine (FTC) Plasma Concentration- Time Plots by Treatment (Linear and Semi-Logarithmic)	Periods Overlaid	SAC		
3.16.	PK Concentration	PKCF3	Median (Range) GSK3640254 Plasma Concentration-Time Plots by Treatment (Linear and Semi-Logarithmic)	Periods Overlaid	SAC		
3.17.	PK Concentration	PKCF3	Mean (± Standard Deviation) Predose (Trough) Tenofovir Alafenamide (TAF) Plasma Concentration Plots by Treatment (Linear and Semi-Logarithmic)	Periods Overlaid	SAC		
3.18.	PK Concentration	PKCF2	Mean (± Standard Deviation) Predose (Trough) Tenofovir (TFV) Plasma Concentration Plots by Treatment (Linear and Semi- Logarithmic)	Periods Overlaid	SAC		

Pharma	Pharmacokinetic: Figures						
No.	Population	IDSL / Example Shell	Title	Programming Notes	Deliverable [Priority]		
3.19.	PK Concentration	PKCF2	Mean (± Standard Deviation) Predose (Trough) Emtricitabine (FTC) Plasma Concentration Plots by Treatment (Linear and Semi-Logarithmic)	Periods Overlaid	SAC		
3.20.	PK Concentration	PKCF2	Mean (± Standard Deviation) Predose (Trough) GSK3640254 Plasma Concentration Plots by Treatment (Linear and Semi-Logarithmic)	Periods Overlaid	SAC		

## 10.9.9. ICH Listings

ICH: Li	stings				
No.	Population	IDSL / Example Shell	Title	Programming Notes	Deliverable [Priority]
Subjec	t Disposition			•	·
1.	Safety	ES3	Listing of Reasons for Study Withdrawal		SAC
2.	Screened	DS7	Listing of Reasons for Screen Failure		SAC
Protoc	ol Deviations				·
3.	Safety	DV2	Listing of Important Protocol Deviations		SAC
4.	Safety	IE3	Listing of Subjects with Inclusion/Exclusion Criteria Deviations		SAC
Popula	tions Analysed				.
5.	Safety	SP3A	Listing of Subjects Excluded from Any Population		SAC
Demog	raphic and Bas	eline Characteris	tics		
6.	Safety	DM2	Listing of Demographic Characteristics		SAC
7.	Safety	DM9	Listing of Race		SAC
Prior a	nd Concomitan	t Medications			·
8.	Safety	CM5	Listing of Concomitant Medications	Based on GSK Drug Dictionary	SAC
Exposi	ire and Treatmo	ent Compliance			·
9.	Safety	EX4	Listing of Exposure Data		SAC
10.	Safety	POP_L1	Listing of Meal Data		SAC
Advers	e Events				
11.	Safety	AE2	Listing of Relationship Between System Organ Class and Verbatim Text		SAC
12.	Safety	AE7	Listing of Subject Numbers for Individual Adverse Events		SAC

ICH: Li	stings				
No.	Population	IDSL / Example Shell	Title	Programming Notes	Deliverable [Priority]
13.	Safety	AE9CP	Listing of All Adverse Events		SAC
Serious	s and Other Sig	nificant Adverse	Events		·
14.	Safety	AE9CP	Listing of Study Drug Related Adverse Events		SAC
15.	Safety	AE9CP	Listing of Serious Adverse Events (Fatal & Non-Fatal)		SAC
16.	Safety	AE14	Listing of Reasons for Considering as a Serious Adverse Event		SAC
17.	Safety	AE9CP	Listing of Adverse Events Leading to Withdrawal from Study		SAC
Hepato	biliary (Liver)				
18.	Safety	MH2	Listing of Medical Conditions for Subjects with Liver Stopping Events		SAC
19.	Safety	SU2	Listing of Substance Use for Subjects with Liver Stopping Events		SAC
All Lab	oratory				
20.	Safety	LB5A	Listing of Clinical Chemistry with any Toxicities		SAC
21.	Safety	LB5A	Listing of All Clinical Chemistry Data for Subjects with any Toxicities		SAC
22.	Safety	LB5A	Listing of Hematology with any Toxicities		SAC
23.	Safety	LB5A	Listing of All Hematology Data for Subjects with any Toxicities		SAC
24.	Safety	LB5A	Listing of Urinalysis with any Toxicities		SAC
25.	Safety	LB5A	Listing of All Urinalysis Data for Subjects with any Toxicities		SAC
ECG					
26.	Safety	EG6	Listing of All ECG Findings		SAC
27.	Safety	EG6	Listing of All Abnormal ECG Findings		SAC
28.	Safety	EG4	Listing of All ECG Values		SAC

ICH: Listings									
No.	Population	IDSL / Example Shell	Title	Programming Notes	Deliverable [Priority]				
Vital Signs									
29.	Safety	VS5	Listing of All Vital Signs of Potential Clinical Importance		SAC				
30.	Safety	VS5	Listing of All Vital Signs for Subjects with any Value of Potential Clinical Importance		SAC				

